### 3.2.2. Secondary Safety Endpoints

- Numbers and proportions of subjects reporting local reactions (pain, erythema, and induration) and their severity, as self-reported on e-diaries for 14 days following the fourth vaccination.
- Numbers and proportions of subjects reporting systemic events (fever, vomiting, diarrhea, headache, fatigue, new or worsening muscle pain, and new or worsening joint pain) and their severity, as self-reported on e-diaries for 14 days following the fourth vaccination.
- Numbers and proportions of subjects reporting AEs from the time of the fourth vaccination up to 28 days after the fourth vaccination categorized according to MedDRA.
- Numbers and proportions of subjects reporting SAEs from the time of the fourth vaccination until 6 months after the fourth dose of vaccine, categorized according to MedDRA.

### 3.3. CCI

- CCI

### 3.4. CCI

CCI

■

■

■

■

■

■

■

- CCI
- [REDACTED]
- [REDACTED]

### **3.5. Safety Endpoints**

#### **3.5.1. Adverse Events**

A 3-tier approach will be used to summarize AEs. Under this approach, AEs are classified into 1 of 3 tiers. Different analyses will be performed for different tiers (see [Section 6.5.1](#)).

Tier 1 events: These are prespecified events of clinical importance and, if any, will be maintained in a list in the product's safety review plan.

Tier 2 events: These are events that are not tier 1 but are “common.” A MedDRA preferred term (PT) is defined as a tier 2 event if there are at least 5% in any vaccine group.

Tier 3 events: These are events that are neither tier 1 nor tier 2 events.

AEs will be captured and reported in accordance with Pfizer reporting standards.

AEs occurring prior to the first vaccination will be excluded from AE analysis, unless the severity increases after dosing. AEs occurring between the informed consent document (ICD) signoff and prior to the first vaccination will be summarized separately.

#### **3.5.2. CCI**

- CCI

#### **3.5.3. Reactogenicity Endpoints**

Reactogenicity data captured in the e-diary consist of local reactions (erythema/redness, induration/swelling, and pain at the injection site), systemic events (fever, vomiting, diarrhea, headache, fatigue, new or worsening muscle pain, and new or worsening joint pain), and use of antipyretics/pain medication to treat symptoms.

### 3.5.3.1. Local Reactions

Local reactions reported in the e-diary are erythema/redness, induration/swelling, and pain.

#### **Local Reactions: Presence or Absence**

The presence of redness or swelling is to be recorded in the e-diary as “Yes” or “No”. If redness or swelling is present, then a second question is to appear requesting the size of the affected area; otherwise, no question is to appear. A measuring device with a scale ranging from 1 to 21 is to be used to measure the largest diameter in whole-number increments. Measurements are to be rounded up to the nearest whole number. If the area is larger than the measuring device can measure, “21+” is to be selected. Measuring device units are converted to centimeters according to 1 measuring device unit = 0.5 centimeters.

The presence of redness and swelling is defined according to the following scale:

- = ., if missing
- = No, if “No” or minimal redness or swelling is present, <2.5 cm (<5 measuring device units)
- = Yes, if  $\geq 2.5$  cm ( $\geq 5$  measuring device units)

These categories (., “No”, “Yes”) will be used for derivation of the variables below.

For the data summary of the presence (“Yes” or “No”) of a local reaction, the following variables for the originally planned stage [first 3 vaccinations] and the extension stage [fourth vaccination] are required:

- Presence (“Yes” or “No”) of each local reaction on each day (Day 1 to Day 7 after the first vaccination on the Day 1, 8, and 30 regimen, and Day 1 to Day 14 after all other vaccinations in both regimens).
- Presence (“Yes” or “No”) of each local reaction on any day (Day 1 to Day 7 after the first vaccination on the Day 1, 8, and 30 regimen, and Day 1 to Day 14 after all other vaccinations in both regimens).
- Presence (“Yes” or “No”) of any local reactions on any day (Day 1 to Day 7 after the first vaccination on the Day 1, 8 and 30 regimen, and Day 1 to Day 14 after all other vaccinations in both regimens).
- Presence (“Yes” or “No”) of each local reaction with severe or greater severity (Grade 3 or Grade 4, as defined in [Table 5](#)) on each day (Day 1 to Day 7 after the first vaccination on the Day 1, 8, and 30 regimen, and Day 1 to Day 14 after all other vaccinations in both regimens).

Table 3 explains the algorithm to derive the presence of a reaction (“Yes” or “No”) during a given time period.

**Table 3. Derived Variables for Each Local Reaction Within a Specified Time Interval**

Variable a	Yes (1)	No (0)	Missing (.)
Any day (Days 1-X)	Subject reports the reaction as “Yes” on any day from Days 1-X	Subject reports the reaction as “No” on all X days or as a combination of “No” and missing on all X days	Subject reports the reaction as missing on all X days

a. The variable will be derived for each of the 3 local reactions (pain, erythema/redness, and induration/swelling), with the time interval Day 1 to Day X after each vaccination. X = 7 days after the first vaccination on the Day 1, 8, and 30 regimen, and X = 14 days after all other vaccinations in both regimens.

For “any local reaction on any day,” a similar rule applies, as specified below in Table 4.

**Table 4. Derived Variables for Any Local Reaction Within a Specified Time Interval**

Variable a	Yes (1)	No (0)	Missing (.)
Any day (Days 1-X)	Subject reports any local reaction as “Yes” on any day from Days 1-X	Subject reports the reaction as “No” on all X days or as a combination of “No” and missing on all X days on all 3 local reactions	Subject reports all of the local reactions as missing on all X days

a. The variable will be derived for Day 1 to Day X after each vaccination. X = 7 days after the first vaccination on the Day 1, 8 and 30 regimen, and X = 14 after all other vaccinations in both regimens.

In addition, each local reaction and any local reaction on any day (Days 1- X) after **any** vaccination in the originally planned phase will be derived, where X = 7 days after the first vaccination on the Day 1, 8 and 30 regimen, and X = 14 days after the second and, third vaccinations on the Day 1, 8, and 30 regimen and after each vaccination on the Month 0, 1, and 6 regimen.

#### **Maximum Severity for Local Reactions**

Erythema/redness and induration/swelling are measured and recorded in measuring device units (range: 1-21+) and then categorized as absent, mild, moderate, or severe based on the grading scale in [Table 5](#). Pain at the injection site will be assessed by the subject as absent, mild, moderate, or severe according to the grading scale in [Table 5](#).

For each local reaction, the maximum severity grade of the reaction will be derived for the e-diary collection period (Day 1 to Day 7 after the first vaccination on the Day 1, 8, and 30 regimen, Day 1 to Day 14 after the second and third vaccinations on the Day 1, 8, and 30 regimen, and Day 1 to Day 14 after each vaccination on the Month 0, 1, and 6 regimen) and

after the fourth vaccination of the extension stage in both regimens. The severity grading scale of the local reaction is presented in Table 5.

The maximum severity will be derived as follows:

- = missing, if all values are missing for all days (Day 1 to Day 7 after the first vaccination on the Day 1, 8, and 30 regimen, and Day 1 to Day 14 after all other vaccinations in both regimens).
- = 0, if the subject reports all reactions as “No”, or a combination of missing and “No” for all days (Day 1 to Day 7 after the first vaccination on the Day 1, 8, and 30 regimen, and Day 1 to Day 14 after all other vaccinations in both regimens).
- = highest grade (maximum severity) within 7 days of vaccination after the first vaccination on the Day 1, 8, and 30 regimen, and within 14 days after all other vaccinations in both regimens, if the answer is not “No” for at least 1 day.

Only an investigator or medically qualified person is able to classify a subject’s local reaction as Grade 4. Grade 4 could also be determined if a reaction is reported as an SAE.

Maximum severity of each local reaction on any day (Days 1- X) after **any** vaccination in the originally planned phase will also be derived, where X = 7 days after the first vaccination on the Day 1, 8 and 30 regimen, and X = 14 after the second, third vaccinations on the Day 1, 8, and 30 regimen and after each vaccination on the Month 0, 1, and 6 regimen.

**Table 5. Local Reaction Grading Scale**

	Mild (Grade 1)	Moderate (Grade 2)	Severe (Grade 3)	Grade 4
Pain	Does not interfere with activity	Interferes with activity	Prevents daily activity	Emergency room visit or hospitalization
Erythema/ Redness	2.5 cm to 5.0 cm (5 to 10 measuring device units)	>5.0 cm to 10.0 cm (11 to 20 measuring device units)	>10 cm (≥21 measuring device units)	Necrosis or exfoliative dermatitis
Induration/ Swelling	2.5 cm to 5.0 cm (5 to 10 measuring device units)	>5.0 cm to 10.0 cm (11 to 20 measuring device units)	>10 cm (≥ 21 measuring device units)	Necrosis

#### **Duration of Each Local Reaction**

The duration of each local reaction will be calculated as the number of days from the start of the first reported reaction to the resolution of the last reported reaction, inclusive. Resolution is the last day on which the reaction is recorded in the e-diary if the reaction lasted 7 days or less for the first vaccination on the Day 1, 8, and 30 regimen or 14 days or less for the second and third vaccinations on the Day 1, 8, and 30 regimen, or 14 days or less for each

vaccination on the Month 0, 1, and 6 regimen, and fourth vaccination of the extension stage in both regimens, or the date the reaction ended if it continues beyond Day 7 for the first vaccination on the Day 1, 8, and 30 regimen and Day 14 for the second and third on the Day 1, 8, and 30 regimen and for each vaccination on the Month 0, 1, and 6 regimen, and fourth vaccination of the extension stage in both regimens, (the latter will be collected on the case report form [CRF]). If there is no known date when the reaction ends, then duration will be missing (unknown). Subjects with no reported reaction have no duration, because it is not applicable. However, the date on which a reaction ended for one vaccination should not be after the beginning of the next vaccination. If a reaction or an event is ongoing at the time of a subsequent vaccination, the duration will be set to unknown.

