### **7.1.1. Electronic Diary**

The subject will be issued an e-diary, based on a smartphone or equivalent technology, and will be asked to monitor and record local reactions, systemic events, and the use of antipyretics/pain medication to treat symptoms for 14 days following vaccination (or 7 days following the first vaccination for subjects on the Day 1, 8, and 30 regimen). The e-diary allows recording of these assessments only within a fixed time window, thus providing the accurate representation of the subject's experience at that time. Data on local reactions, systemic events, and use of antipyretics/pain medication to treat symptoms reported on the e-diary will be transferred electronically to the e-diary vendor, where they will be available for review by investigators and the Pfizer clinicians at all times via an Internet-based portal. E-diary data review is ongoing during subject e-diary data-entry periods (7 days after the first vaccination and 14 days after the second, third, and fourth [if applicable] vaccinations) via an Internet-based portal.

At intervals agreed to by the vendor and Pfizer, these data will be transferred electronically into Pfizer's database for analysis and reporting. These data do not need to be reported by the investigator in the CRF.

Investigators (or designee) will be required to review the e-diary data online at frequent intervals as part of the ongoing safety review.

The investigator or designee must contact the subject in order to obtain stop dates for any ongoing local reactions or systemic events or continuing use of antipyretic/pain medication to treat symptoms on the last day that the e-diary was completed. The stop dates should be documented in the source documents and the information entered in the CRF.

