- Maximum severity of each systemic event on any day (Day 1 to Day 7 after the first vaccination on the Day 1, 8 and 30 regimen, and Day 1 to Day 14 after all other vaccinations in both regimens).
- Duration of each systemic event.
- Onset day of each systemic event since the last vaccination.

The algorithm for deriving the presence of a systemic event (“Yes” or “No”) during Day 1 to Day 7 after the first vaccination on the Day 1, 8, and 30 regimen or during Day 1 to Day 14 after all other vaccinations in both regimens is similar to that in [Table 3](#) and [Table 4](#) for local reactions. For the purposes of deriving the variable “any systemic event on any day” (Day 1 to Day 7 after the first vaccination on the Day 1, 8, and 30 regimen or Day 1 to Day 14 after all other vaccinations in both regimens), for each day, a systemic event including fever, vomiting, diarrhea, headache, fatigue, new or worsening muscle pain, or new or worsening joint pain will be included as one of the possible systemic events.

In addition, similarly to local reactions, each systemic event, any systemic event, and maximum severity of each systemic event on any day after **any** vaccination in the original planned phase will be derived.

As stated before, only temperature data between 35.0°C and 42.0°C will be used for derivation of fever (“Yes” or “No”) in “any systemic event on any day.” The variable of “any systemic event on any day” will be derived similarly as “any local reaction on any day” based on the rule stated in [Table 3](#). The duration of each systemic event and the onset day of each systemic event since the last vaccination are derived similarly as the rules stated above for local reactions. Antipyretics/pain medication used to treat symptoms will be handled separately and will not be considered as systemic events.

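### When an e-diary stops early with a reaction ongoing, the SAP's duration rule passes over a CRF stop date that falls inside the diary window and scores the reaction too short

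*SAP*

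**What the plan says.** SAP 3.5.3.1 (Duration of Each Local Reaction) counts days from first report to resolution, inclusive, and gives resolution two branches.

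- **Diary branch.** For Dose 1 of the Day 1, 8, and 30 regimen: "Resolution is the last day on which the reaction is recorded in the e-diary if the reaction lasted 7 days or less". The cut-off is "14 days or less for the second and third vaccinations on the Day 1, 8, and 30 regimen", and the same 14 days apply to each Month 0, 1, and 6 dose and to Dose 4.
- **CRF branch.** Resolution is "or the date the reaction ended if it continues beyond Day 7 for the first vaccination on the Day 1, 8, and 30 regimen", with Day 14 as the limit for all other doses. The SAP describes only this second date as coming from the CRF.

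Two fallbacks follow. The first is "If there is no known date when the reaction ends, then duration will be missing (unknown". The second is "If a reaction or an event is ongoing at the time of a subsequent vaccination, the duration will be set to unknown".

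SAP 3.5.3.2 carries the rule over: "The duration of each systemic event and the onset day of each systemic event since the last vaccination are derived similarly" to local reactions. SAP 3.5.4 does the same for antipyretic and pain medication use. SAP 6.5.2 reports descriptive statistics of duration.

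On collection, Protocol 7.1.1 says the investigator or designee "must contact the subject in order to obtain stop dates for any ongoing local reactions or systemic events", and for continuing medication use, still present on the final diary day completed. These dates are entered in the CRF. That paragraph does not restrict the trigger to Day 7 or Day 14.

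**The concern.** The protocol's trigger for collecting a stop date and the SAP's trigger for using it differ. The protocol's is the last completed diary day. The SAP's is the scheduled end of the diary window. They coincide when the diary is kept to the end. They part when a subject stops entering data while a reaction is present and the reaction then ends before the window closes. In that case the SAP treats the end of diary keeping as the end of the reaction, although the protocol has asked for the true date.

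Early stopping is foreseeable. Protocol 7.1.1 accepts entries only within a fixed time window, so missed days cannot be filled in later. SAP 3.6.1 has completion categories down to 0 to 3 complete days out of 14. SAP 5.3.2 treats a period with any one diary day available as nonmissing.

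What is at stake is the accuracy of the duration summaries, in a trial whose rationale includes local reactogenicity seen with another formulation.

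**Working it through.** **No figure to reproduce.** This is a derivation rule and the plan attaches no number to it, so I applied the rule as written.

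**Notation.** s = onset day, d = last diary day on which the reaction is recorded (the diary stops there), e = CRF stop day, X = 7 or 14.

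- SAP duration = d − s + 1 if e ≤ X; e − s + 1 if e > X.
- Duration from the collected stop date = e − s + 1.
- Shortfall when d < e ≤ X: e − d days.

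**Examples**

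| X | s | d | e | SAP rule | From CRF date |
|---|---|---|---|---|---|
| 14 | 2 | 5 | 9 | 5 − 2 + 1 = 4 | 9 − 2 + 1 = 8 |
| 14 | 1 | 3 | 10 | 3 | 10 |
| 14 | 1 | 3 | 14 | 3 | 14 |
| 14 | 1 | 3 | 15 | 15 | 15 |
| 7 | 1 | 3 | 7 | 3 | 7 |
| 7 | 1 | 3 | 8 | 8 | 8 |

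One extra day of reaction, Day 14 to Day 15, moves the SAP value from 3 to 15.

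**All patterns.** Enumerating every s ≤ d < e ≤ X gives 455 patterns for X = 14 and 56 for X = 7. The SAP value is shorter in all of them, by 1 to 13 days and 1 to 6 days respectively. These count possible patterns, not expected frequencies.

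**Do the fallbacks catch the case?** The unknown-date sentence does not, because e is known. Nor does the next-vaccination sentence. In 14-day periods the shortest gap to another dose is 20 days (Protocol 6.1.4), so a reaction over by Day 14 cannot be ongoing then. In the 7-day period, Dose 2 comes at least 7 days after Day 1, that is Day 8 or later, so a reaction over by Day 7 is not ongoing then either.

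**Effect on a group mean.** The documents give no rate of early diary stopping, so these inputs are assumptions: 14-day diary, onset uniform on Days 1 to 3, geometric duration with mean 2 to 5 days, constant daily drop-out q. The share abandoning the diary within 14 days is 1 − (1 − q)^14.

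| q | Abandon within 14 days | Fall in mean duration, all reactions |
|---|---|---|
| 1% | 1 − 0.99^14 = 13% | about 1–2% |
| 2% | 1 − 0.98^14 = 25% | about 2–4% |
| 5% | 1 − 0.95^14 = 51% | about 5–10% |

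Affected reactions are scored at about half their length: 2.7 against 5.5 days when the mean is 3 days, and 3.5 against 7.1 when it is 5. Restricting the mean to reactions ending by Day 14 gives larger relative falls: at q = 2% and a 5-day mean, 4.24 to 4.01 days, or 0.23/4.24 = 5.4%. SAP 6.5.2 does not restrict its summaries in that way, so the table is the relevant one.

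**The case against.** **The stop date may not exist.** The event-specific text in Protocol 7.1.1.2, 7.1.1.3 and 7.1.1.4 ties extra CRF entry to events lasting past the end of the diary period, and SAP 3.5.3.2 mentions a CRF stop date for fever only at Day 7 or Day 14. On that view, the last completed day in Protocol 7.1.1 means the last scheduled day, and an early stop yields no date. This stands in part: one cannot assert that the date is in the database. But Protocol 7.1.1 contains no such limit, and no other text settles it.

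**It matters little.** Duration is not in the primary or secondary safety endpoint lists (SAP 3.1.2 and 3.2.2), no decision rule uses it, and diary completeness is reported separately. Sites also review diaries online and remind subjects at the visit 7 to 11 days after most doses. This stands, and it sets the severity.

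**Stronger readings that the documents do not support**

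- A reader might infer that every reaction over by Day 14 is misscored. With a complete diary, the last recorded day is the correct end.
- A reader might infer that the longest reactions suffer most. Those running past the window take the CRF date and are unaffected.
- A reader might infer that, with no stop date obtained, the rule still returns a number. The diary branch requires that the reaction lasted no more than 7 or 14 days. That cannot be verified if the diary stops with the reaction present, and the unknown-date sentence is the ordinary reading. The two sentences should still be reconciled explicitly.

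**Conclusion.** The concern holds for one case: the diary stops early with the reaction present, and a CRF stop date on or before Day 14 (Day 7 for Dose 1 of the Day 1, 8, and 30 regimen) was collected. The SAP then understates duration, always in the same direction. Systemic events and medication use inherit the error. Presence, severity and the erythema safety review rule do not depend on duration and are untouched.

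A single affected record can be well out, but group means move by a few percent unless diary abandonment is heavy; the 5% scenario supposes that half the subjects give up a 14-day diary. The size rests on the assumed drop-out rates and durations, and on reading Protocol 7.1.1 as covering early stops. The direction follows from the text of the rule. This is a minor point, worth considering at the next SAP revision.

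**What to change.** In SAP 3.5.3.1, and by reference in 3.5.3.2 and 3.5.4, replace the two resolution branches with:

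> If the reaction is present on the last completed e-diary day, on whichever day that falls, resolution is the CRF stop date; if no CRF stop date is available, duration is unknown. Otherwise resolution is the last e-diary day on which it is recorded.

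Keep the existing sentence on reactions ongoing at the next vaccination. The new wording covers the 7-day and 14-day periods alike. It also settles a reaction such as Day 5 to Day 16, which lasts 12 days yet continues past Day 14 and so meets both present branches.

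Confirm, too, that the last completed diary day in Protocol 7.1.1 includes diaries that stop early, and align Protocol 7.1.1.2 to 7.1.1.4 and the fever text in SAP 3.5.3.2 with the answer.

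Cost: one SAP sentence and a small programming change, with no new data collection if Protocol 7.1.1 is applied literally. A few durations become longer or unknown.

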### **3.5.4. Antipyretics/Pain Medication Use**

The following variables will be derived for the use of antipyretics/pain medication to treat symptoms:

- Medication use to treat fever or pain on each day (Day 1 to Day 7 after the first vaccination on the Day 1, 8, and 30 regimen, Day 1 to Day 14 after all other vaccinations in both regimens).
- Medication use to treat fever or pain on any day (Day 1 to Day 7 after the first vaccination on the Day 1, 8, and 30 regimen, Day 1 to Day 14 after all other vaccinations in both regimens).
- Duration of medication use to treat fever or pain.

- Onset day of medication use (since the last vaccination) to treat fever or pain.

Duration of medication use to treat fever or pain and onset day of medication use (since the last vaccination) to treat fever or pain are derived similarly as the rules stated above for local reactions.

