## 5.2. General Methods

Unless otherwise explicitly stated, descriptive statistics for continuous variables are n, mean, median, standard deviation, minimum, and maximum. Descriptive statistics for categorical variables are the percentage (%) and the numerator (n) and the denominator (N) used in the percentage calculation.

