#### **5.3.2. Safety Data**

Handling of missing information related to safety data, such as missing or partially missing date, will be in accordance with Pfizer reporting standards.

For derived variables in reactogenicity data, if any day of the 7-day e-diary is available, the “Day 1 – Day 7” data will be considered as nonmissing for analyses after Vaccination 1 on the Day 1, 8, and 30 regimen and if any of the 14-day e-diary is available, the “Day 1 – Day 14” data will be considered as nonmissing for analyses after Vaccinations 2 and 3 on the Day 1, 8, and 30 regimen, and after each vaccination on the Month 0, 1, and 6 regimen, and Vaccination 4 in the extension stage. The proportion of subjects with missing reactogenicity data will also be summarized by each vaccination for each vaccine group. The denominator will be the number of subjects who receive the scheduled vaccination.

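### Minor: setting a duration to unknown when the reaction reaches the next vaccination is expected to understate the mean and maximum Dose 1 durations in the Day 1, 8, 30 regimen

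*SAP*

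**What the plan says.** SAP 3.5.3.1 (Duration of Each Local Reaction) defines duration as "calculated as the number of days from the start of the first reported reaction to the resolution of the last reported reaction, inclusive". For reactions that outlast the diary after Dose 1 of the Day 1, 8, 30 regimen, the end is "the date the reaction ended if it continues beyond Day 7 for the first vaccination on the Day 1, 8, and 30 regimen", taken from the CRF. The paragraph then adds that "the date on which a reaction ended for one vaccination should not be after the beginning of the next vaccination", and closes with "If a reaction or an event is ongoing at the time of a subsequent vaccination, the duration will be set to unknown".

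The same derivation is used elsewhere. SAP 3.5.3.2 states: "The duration of each systemic event and the onset day of each systemic event since the last vaccination are derived similarly as the rules" given for local reactions. SAP 3.5.4 says that duration and onset day of medication use "to treat fever or pain are derived similarly as the rules stated above for local reactions".

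SAP 6.5.2 plans descriptive statistics of maximum duration, and SAP 5.2 sets the default: "descriptive statistics for continuous variables are n, mean, median, standard deviation, minimum, and maximum". Neither section mentions censoring. SAP 5.3.2 says: "The proportion of subjects with missing reactogenicity data will also be summarized by each vaccination for each vaccine group".

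Dose 2 follows Dose 1 by 7 to 11 days in the Day 1, 8, 30 regimen (Protocol 6.1.2), and Dose 3 follows Dose 2 by 20 to 26 days (6.1.4). In the Month 0, 1, 6 regimen Dose 2 follows by 25 to 35 days (6.2.2). A persisting site reaction does not by itself hold up Dose 2 in the Day 1, 8, 30 regimen; the injection goes into the other arm (Protocol 5.5.3, 6.1.2).

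**The concern.** Whether a duration is missing depends on the duration itself. Among reactions starting on the same day, those that last to the next dose are dropped and shorter ones are kept. An ordinary mean and maximum of what remains describe short reactions only. With a gap of 7 to 11 days this can take effect after Dose 1 of the Day 1, 8, 30 regimen; with 20 days or more it hardly can. A reader comparing Dose 1 durations between regimens would then see some difference produced by the rule rather than by the vaccine.

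The number removed is also not clearly visible. Reactors minus the duration n gives all unknown durations together, without separating reactions still present at the next dose from those with no stop date obtained.

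**Working it through.** The plan states no duration figure, so there is none to reproduce. The check asks what the rule does under assumed durations.

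**Inputs from the documents.** Gap g to the next dose: 7-11, 20-26 or 25-35 days. Durations are inclusive whole days and vaccination is on Day 1. There are 183 subjects per active group (Protocol Table 1). Phase 1 rate of any local reaction after Dose 1: 16.7% (aluminum hydroxide, 200 µg, ages 65 to 85; Protocol 1.2.3).

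**Assumptions, not in the documents.** Onset on Day 1; gaps spread evenly over the window; true mean m of 2, 3 or 5 days; the shapes named below.

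**Cap.** A gap of g days puts the next dose on Day g+1. With onset on Day 1, a duration d is kept if d ≤ c, where c = g if the reaction must end before that day and c = g+1 if an end on that day is accepted. The SAP leaves this open. For g = 7 to 11 the longest duration kept is therefore 7 to 11, or 8 to 12, days.

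**Geometric durations.** With q = 1 − 1/m:
- share lost = average over g of q^c
- mean kept = (m − average of q^c × (c + m)) / (1 − share lost)

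Example, m = 3, c = 7 to 11:
- q^c = 0.0585, 0.0390, 0.0260, 0.0173, 0.0116; average 0.0305, so 3.05% are lost.
- q^c × (c + 3) averages 0.3428.
- Mean kept = (3 − 0.3428) / 0.9695 = 2.74, which is 8.6% too low.

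In each cell the first figure requires an end before the day of Dose 2 and the second accepts an end on that day.

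| True mean | Share lost | Error in mean | Median, true → reported |
|---|---|---|---|
| 2 days | 0.30% / 0.15% | −1.2% / −0.7% | 1 → 1 |
| 3 days | 3.05% / 2.03% | −8.6% / −6.4% | 2 → 2 |
| 5 days | 14.1% / 11.3% | −28.1% / −24.3% | 4 → 3 |

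**Other shapes, same gaps.**
- Narrower (1 + Poisson): mean 3, −0.2% / −0.1%; mean 5, −3.5% / −1.8%.
- Wider (1 + negative binomial, variance/mean 5): mean 2, −11% / −9%; mean 3, −18% / −15%; mean 5 coincides with the geometric.

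**Other intervals, geometric, mean 5.**
- 20-26 days: 0.65% / 0.52% lost, mean −2.9% / −2.4%.
- 25-35 days: 0.16% / 0.13% lost, mean −0.9% / −0.7%.

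**Absolute count.** 183 × 0.167 = 30.6, about 31 reactors per active group. Expected losses are 31 × 0.0030 = 0.09 (mean 2), 31 × 0.0305 = 0.95 (mean 3) and 31 × 0.141 = 4.4 (mean 5); accepting a same-day end gives 0.05, 0.63 and 3.5. That is roughly 0 to 4.

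**Direction is not guaranteed.** Suppose 80% of reactions start on Day 1 and last 5 days, 20% start on Day 7 and last 2, Dose 2 is on Day 8, and a same-day end is not accepted. The true mean is 0.8 × 5 + 0.2 × 2 = 4.4; the kept mean is 5.0. Late, short reactions can be the ones removed.

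**The case against.** The rule has a sensible motive. After Dose 2, an ongoing systemic event or use of pain medication cannot readily be assigned to Dose 1, and injection-site diary entries then refer to the new dose only (Protocol 6.1.2). This argues against using a stop date that falls after Dose 2. It does not argue against recording that the reaction lasted at least until Dose 2, which needs no attribution.

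The reach is limited, and this stands. Duration is in no primary or secondary safety endpoint, there are no hypothesis tests, and the median barely moves. Febrile illness delays dosing (Protocol 4.5), so fever is little affected. A confirmed related Grade 3 or 4 local reaction ends vaccination for that subject (Protocol 7.1.1.2), so its duration is not blanked by this rule; nor are durations capped at 7 to 11 days where Dose 2 is delayed. The loss falls mainly on persistent mild and moderate reactions.

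A reader might infer that SAP 5.3.2 certainly leaves these cases uncounted. That is the likelier reading, because the paragraph turns on diary availability and uses vaccinated subjects as denominator. But it opens by referring to derived reactogenicity variables, and duration is one, so the text does not settle it.

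**Conclusion.** The point holds as a minor one. Followed as written, the rule truncates Dose 1 durations in the Day 1, 8, 30 regimen. The reported mean and maximum are expected, though not certain, to be too low and not comparable with those of the Month 0, 1, 6 regimen. The maximum escapes if a subject with no Dose 2 or a delayed one has the longest reaction.

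The mechanism is firm; the size is not. At a true mean of 5 days the error in the mean runs from 1.8% to 28% depending only on the assumed spread and the same-day reading. At 2 days it is about 1% if geometric and 9-11% if wider.

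Two stronger inferences are not supported. One is that durations will be understated by about a quarter: that needs both a mean near 5 days and a long tail, and the documents give no duration data. The other is that the safety conclusions are biased: occurrence, severity, onset and immunogenicity do not use this rule, and no planned decision is shown to rest on duration.

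**What to change.** Replace the last sentence of the duration rule in SAP 3.5.3.1, with the same effect in 3.5.3.2 and 3.5.4:

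- Right-censor a duration still running at the next vaccination at that date, and list it as ≥ x days.
- Make a Kaplan-Meier median the main duration summary. Label any mean, SD and maximum as based on completed durations only.
- Report, by dose and vaccine group, the number and percentage of reactions and events ongoing at the next vaccination, separately from other unknown durations where the collected data allow. Sites follow up ongoing events at Visit 2 and seek stop dates (Protocol 6.1.2, 7.1.1), but the documents do not say that ongoing status at Dose 2 is its own CRF field.
- State whether an end on the day of the next vaccination counts as known.
- Optionally, for local reactions where the next injection went into the opposite arm, add a sensitivity summary using the CRF stop date. The sentence limiting end dates to the next vaccination would need an exception. This should stay a sensitivity summary: in the Day 1, 8, 30 regimen the opposite arm is the protocol's default for a persisting site reaction, so as a main rule it would largely displace the censoring.

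The cost is SAP wording, minor programming and slightly longer reported durations. No new data collection is proposed.
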